Qualitative feedback re-enforces the challenges with communication within the department, particularly among different staff groups:

"Communication within the department is not straightforward - there is a gap between nursing and doctoring staff, which means that often as staff members we are not aware of what is truly going on within the department, particularly in terms of improvement projects."

This highlights a potential area for improvement within NZ EDs that may be challenging to implement but seems relatively low-cost and is potentially beneficial to staff morale and quality of patient care.

System-Level Interventions

As outlined above, while there is evidence for improvement in wellbeing with individual-focussed positive psychology interventions (PPIs), such as mindfulness, and PPIs^{46,62} a systems approach is considered necessary to sustain HCW wellbeing at scale.^{20,28,29,63,64}

Despite examination of evidence and calls for investment in organisation level research, consistent and specific recommendations for systems interventions have been lacking.²⁰ As well, recommendations such as imploring HCOs to invest in and prioritise HCW wellbeing by, for example, encouraging clinician leadership and having dedicated clinician Chief Wellbeing Officers rely upon board level decision making.⁶⁵⁻⁶⁷ While ownership of what is in one's sphere of influence is called for, many system-level decisions and changes are out of the control of most frontline workers such as ED staff.

Following lessons from the COVID-19 pandemic, a 2022 advisory from the US surgeon general makes several recommendations.³³ One such recommendation is "*Transform workplace culture to empower health workers and be responsive to their voices and needs.*"(page 21) Another is "*Show health workers how much they are valued.*"(page 21) While these are laudable, logical and much needed aspirations, how are such recommendations to be achieved, particularly in settings with high levels of staff burnout¹¹ a stretched financial situation and major changes in the NZ health system?

Improving Quality of Care

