Training in Quality Improvement (QI) methods, with an emphasis on the local and ED contextual factors, will be delivered by an expert in QI training. Training will be delivered online. Individual and group coaching will be delivered by trained QI coaches. Monthly meetings of all LCG personnel will be opportunities to share lessons and build camaraderie required for sustainability. Further details of the training and coaching components are found elsewhere.

Local Champions Group

A Local Champions Group (LCG) will be critical to success at each site. The LCG will have up to 5 personnel and be a diverse composition of the local ED team, including one or more of senior doctors, nurses, other ED team members, consumers, and mana whenua. The LCG will be in the best position to understand local needs, liaise with local leaders, liaise with the investigators, and oversee many parts of the intervention in their ED. Each member of the LCG will attend the training and coaching program.

The study website

The study website provides a repository of important information for all those involved in the research. Established in 2020 and hosted by Squarespace, the website can be accessed via QR code or via the web address (www.woweated.com).

Access to open and password protected pages enables different groups access to relevant information. Participant information including about the various individual-level interventions will be available to participants, accessible via a QR code or the web address. Electronic links will allow participants to provide informed consent and access the intervention of their choice. In addition, Local Champions will have access to other information, for example group-level intervention information and links, and requirements for QI training and coaching.

The site will be maintained and modified by the PI, with advice from our University of Auckland IT specialist when required.

Study Design

A prospective multisite before and after study, using mixed methods, of the multicomponent intervention package in NZ EDs. The logistics of introducing a complex intervention into a series of EDs make compliance with randomisation, as in a randomised stepped wedge cluster study, impractical and unrealistic.

Study Setting

Individual NZ Emergency Departments will be the setting.

Site Selection

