 - patient did not wait rates, and
 - ED length of stay (LOS) over intervention year.
 - Seasonally adjusted daily staff absence, vacancies, monthly resignations, and Bradford Scale Score.
 - Compliance with the 6 targets of Te Tumu Whakarae for Māori workforce development.¹⁰²

Participants

Sample Size

Power

Differences of ≥ 5 on the CBI work-related burnout scale are considered clinically significant.¹² A sample size of 900 staff participants over 8 EDs will have 90% power to detect a change of ≥ 5 (2-tail $\alpha=0.05$).

Recruitment

Site selection is discussed above. All staff at each study site are eligible for the interventions. Participation of staff will rely upon local champions. REDCap Public Survey Links for survey distribution to participants will be used to maximise usability, anonymity and the ability to collect data. Participation by staff will be voluntary.

Māori Participation

Recruiting and retaining a Māori ED health workforce is fundamental to the advancement of Māori health and are tenets of the Ministry of Health He Korowai Oranga framework, the ACEM Te Rautaki Manaaki Mana (Māori Health Strategy),⁶ and the Māori Workforce development targets agreed to by DHBs.¹⁰² While Māori are currently under-represented in the NZ ED workforce, by maximising workplace wellbeing and reducing burnout, staff and patients benefit, particularly Māori, who most stand to benefit by health systems that are responsive to Māori needs and healthcare aspirations now and far into the future. The team has active involvement of experienced Māori emergency care leaders in clinical care, advocacy and research.

Interventions that may benefit Māori staff and patients can be undertaken by participating individuals and departments. For example, an area for improvement related to Te Ao Māori may be identified by staff, and an improvement program undertaken.

Timeframe

Implementation

Two waves of implementation will begin in March 2023 and 2024 respectively. Each wave will have between three and five EDs. Lessons learned from wave 1 will inform the implementation of interventions in wave 2. The intervention and study periods will be for 12 months.

Data collection

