Via RedCAP survey software. Staff survey at baseline (demographics: age range, gender,¹⁰³ work group, ethnicity,¹⁰⁴ years of experience at current ED) and 12 months of CBI and other measures. Routine ED data for triage compliance, did not wait rate, ED LOS, staff absence and resignations and Te Tumu Whakarae targets.

Analysis

Statistical methods

The primary and secondary outcomes will be compared pre and post intervention using a general linear mixed model with site as a random factor. Additional analyses of the primary outcome will be undertaken based on workforce group (nurse vs. other), and ethnicity (Māori vs. non-Māori), to test for differential effects of the intervention among these subgroups.

Longitudinal measurement of outcomes for individuals, that is, data-linkage and comparing results from the pre-and post-intervention surveys, is required for robust assessment of effects of the intervention. Balanced with the need for robust assessment is the need for participant confidentiality.

[figure not shown]
REDCap Public Survey Links for survey distribution to participants will be used to maximise usability, anonymity and the ability to collect data. The answers to the following two questions will be individually consistent, enabling data-linkage of coded participant data.

The screenshot shows two separate survey questions in a REDCap interface. The first question is 'What is the name of your first primary school' with a text input field. The second question is 'In which year was your mother born?' with a text input field. Both questions have a toolbar above them with icons for edit, copy, paste, and delete, and a label 'Variable: first_primary_school' and 'Variable: mother_birth_year' respectively. Below each question are buttons for 'Add Field', 'Add Matrix of Fields', and 'Import from Field Bank'.

Figure 1 Two data points for data linkage

A Public Survey Link will again be used to distribute the post-intervention survey. Respondents will be asked if they participated in the pre-intervention survey. All demographic questions will be the same as the pre-intervention survey.

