Participant information will be available online prior to consent, as well as presented at engagement meetings. Electronic consent will be required of all participants prior to participation.

Confidentiality

No identifiable features will be captured via REDCap

Declaration of interests

No member of the research team has any conflicts to declare.

Access to data

Electronic data are stored in password-controlled computers and cloud storage. Data are accessible to the PI and statistician.

Dissemination policy

Dissemination of findings will primarily be through publication in peer-reviewed journals, and presentation at national and international hui and scientific meetings. Individual site feedback will be provided to each participating ED, and hospital executive leadership.

Further dissemination priorities will include:

- potentially national roll-out via the NZEMN if intervention successful
- potentially national roll-out via the HQSC to other hospital areas if intervention is successful
- writing commentaries and editorials in which the research findings can be further disseminated, via established links with international journals, and
- presenting findings to lay audiences through established media links.

References

1. HQSC. Engaging With Consumers. A guide for district health boards. Health Quality & Safety Commission, 2015.
2. WHO. ICD-11. (<https://icd.who.int/browse11/l-m/en#/http://id.who.int/icd/entity/129180281>).
4. ACEM. Standard Terminology for Emergency Departments Policy (P02). Australasian College for Emergency Medicine; 2019.
5. ACEM. Quality Standards for Emergency Departments and Hospital-Based Emergency Care Services. <https://acem.org.au/Content-Sources/Advancing-Emergency-Medicine/Better-Outcomes-for-Patients/Quality-Standards2022>.
6. ACEM. Te Rautaki Manaaki Mana Excellence in Emergency Care for Māori. 2019.
8. HQSC. Mō mātou About us Health Quality and Safety Commission. (<https://www.hqsc.govt.nz/about-us/>).

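### The planned pre-post comparison cannot separate the package's effect from a trend in burnout common to both study years, so its result should be reported as change, with the staggered waves used only as caveated support.

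*Protocol*

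**What the plan says.** Under Study Design the protocol describes "A prospective multisite before and after study, using mixed methods, of the multicomponent intervention package in NZ EDs". It explains why there is no randomisation: the logistics "make compliance with randomisation, as in a randomised stepped wedge cluster study, impractical and unrealistic". It does not discuss a non-randomised comparison with sites that are still waiting.

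Under Timeframe, Implementation: "Two waves of implementation will begin in March 2023 and 2024 respectively". "Each wave will have between three and five EDs", and "The intervention and study periods will be for 12 months". Data collection places the staff survey at each site's baseline and at 12 months. The wave 1 follow-up and the wave 2 baseline therefore both fall around March 2024.

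Under Statistical methods: "The primary and secondary outcomes will be compared pre and post intervention", by a general linear mixed model with site as a random factor. No wave, calendar-time or concurrent term is named there.

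The primary research question (Table 8) asks whether the package improves burnout, and Statistical methods speaks of the effects of the intervention. System-Level Interventions describes the setting as "a stretched financial situation and major changes in the NZ health system". Site Selection states that departments which put themselves forward, have stable leadership and are readiest to change are taken first.

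**The concern.** The question is causal, but the stated comparison sets each site only against its own past. A random site factor absorbs differences in level between sites; it does not remove a movement shared by all of them. If burnout among emergency staff shifts nationally over the study years, that shift enters the estimate with the same standing as the package's effect. A fall would look like benefit and a rise would hide it. With several hundred respondents per survey, even a shift well below the protocol's own threshold of 5 points can be statistically significant. The protocol itself points to a health system undergoing change, so a stable background cannot be taken for granted.

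**Working it through.** **Inputs.** From the protocol: 900 staff, 8 departments, 90% power for 5 points, two-sided 0.05 (Power); SD 19.1 for the work-related CBI score (Table 5, 2020 national survey). Assumed, because the protocol gives none: drift size, within-person correlation r, number of linked pairs, ICC, and SD of true change between sites (τ).

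**The plan's own figure.** With SD 19.1, two independent surveys need 2 × (1.960 + 1.282)² × 19.1² / 5² = 307 each, 614 in total, not 900. The inputs behind 900 are not stated, so it is not reproduced. This is a separate matter and does not show that 900 is too small. Here 900 serves only to set the standard error.

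**What the planned surveys can identify.** Let a1 and a2 be the wave levels in March 2023, p24 and p25 the common shifts from March 2023 to March 2024 and to March 2025, and θ the effect.

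| | March 2023 | March 2024 | March 2025 |
|---|---|---|---|
| Wave 1 | a1 | a1 + p24 + θ | – |
| Wave 2 | not surveyed | a2 + p24 | a2 + p25 + θ |

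- Within-wave changes are θ + p24 and θ + (p25 − p24): two quantities, three unknowns. In matrix terms, the four cells have rank 4 for 5 parameters (rank 3 for 4 with linear time).
- The pooled estimate is θ plus the wave-weighted mean of the two yearly shifts. With equal waves, a shift of d confined to one year contributes d/2. A steady trend of d per year contributes all of d.
- The March 2024 difference between waves is θ + (a1 − a2). If site levels are random with a common mean, this is the only source that identifies θ once a calendar-period term is fitted.
- Adding wave 2 in March 2023 supplies a2. The rank becomes 5 of 5, and the difference-in-differences equals θ if the trend is common to both waves.

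**Drift with zero effect.** SE = 19.1 × √(2(1 − r)/n).
- 900 linked pairs, r = 0.5: 19.1/√900 = 0.64.
- 450 linked pairs, r = 0.5: 19.1/√450 = 0.90. For 900 + 900 unlinked responses, 19.1 × √(2/900) = 0.90.

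P(p<0.05) ≈ Φ(drift/SE − 1.96):

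| Drift (points) | SE 0.90 | SE 0.64 |
|---|---|---|
| 1 | 20% | 35% |
| 2 | 60% | 88% |
| 3 | 92% | 99.7% |

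A 2-point drift seldom produces an estimate of 5: (5 − 2)/0.90 = 3.3 standard errors away, and further at SE 0.64.

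**Precision of the March 2024 contrast** (4 against 4 sites, 900/8 = 112.5 staff per site). SE = √{[ICC × 19.1² + (1 − ICC) × 19.1²/112.5] × (1/4 + 1/4)} = 1.85, 2.29 and 3.27 for ICC 0.01, 0.02 and 0.05. Power for 5 points on t with 6 df: 62%, 45% and 25%.

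**Precision of a difference-in-differences.** SE = √{[τ² + 2(1 − r) × 19.1²/112.5] × (2/4)}, r = 0.5: 1.46, 1.90 and 2.47 for τ = 1, 2 and 3.

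**The case against.** Several points on the other side stand.

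- **Drift is assumed.** The only repeated CBI figures in the protocol are for NZ senior medical officers in Table 5: work-related burnout of 42.0% in 2015 and 43.5% in 2020. That is a small rise over five years, in another population and an earlier period. A reader might infer that burnout is falling after the pandemic and that a favourable result would be mostly recovery. The protocol does not say so, and financial strain and system change could as well point to worsening.
- **Not every shift counts in full.** One confined to a single year is diluted by pooling.
- **Significance is not the protocol's clinical threshold.** A 2-point drift would rarely reach 5 points. The SEs of 0.64 and 0.90 also leave out site-to-site variation in change. With τ = 2 over 8 sites, 0.64 becomes √(0.637² + 2²/8) = 0.95, and 88% becomes Φ(2/0.95 − 1.96), about 56%.
- **The concurrent comparison is weak.** A reader might infer that wave 2 offers a ready control whose agreement would confirm an effect. Site Selection does not support that: early adopters go first, so a1 − a2 need not be zero, and adjustment for work group does not remove differences in readiness. With zero effect and exchangeable waves, the contrast favours wave 1 half the time. With an assumed 3-point baseline advantage it does so 82% (Φ(3/3.28)) to 90% (Φ(3/2.30)) of the time. Start dates are set site by site, expected within about 2 months of the engagement visit, so the surveys coincide only roughly.
- **The extra survey may not be possible.** Nothing shows that wave 2 sites are known in March 2023.
- **Roll-out is tentative.** The Dissemination policy lists "potentially national roll-out via the NZEMN if intervention successful"; it contains no decision rule.
- **The analysis plan is not at hand.** A calendar term may be specified there, and its absence from the protocol is not an error. Such a term cannot cure the problem within sites, however: survey timing and the causal wording are set in the protocol.

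**Conclusion.** The point holds in a limited form. The stated pre-post comparison cannot distinguish the package's effect from a trend common to both study years, whichever way the trend runs. This follows from the design and needs no assumption. The size does: with zero effect, a 2-point fall would reach p<0.05 in about 60% to 88% of trials under r = 0.5, SD 19.1, and either 450 to 900 linked pairs or 900 unlinked responses per survey. The lower end would drop further if the test allowed for variation in change between sites.

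The documents do not support the stronger reading that drift of this size is expected, or that the March 2024 contrast would settle the matter. That contrast is supportive evidence only. The before-and-after design is openly declared and the lack of randomisation explained; what needs changing is the claim attached to the result and the use made of the stagger.

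**What to change.** 1. Report the pooled before-and-after result as change over 12 months, not as an effect of the intervention, and state that secular trend is not excluded.
2. Pre-specify as a supportive analysis a model over both waves with a calendar-period term or, equivalently, the contrast around March 2024 of wave 1 at 12 months with wave 2 at baseline. Adjust for work group and report the interval. State that the contrast is non-randomised, confounded by early-adopter selection, only roughly concurrent and imprecise (SE about 2.3 to 3.3 for assumed ICC 0.02 to 0.05). Do not use its direction alone as a gate for claiming an effect.
3. Only if wave 2 sites are already identified, consider one online survey there in March 2023, so that a difference-in-differences estimate (SE about 1.5 to 2.5, assumed inputs) can be the key supportive analysis. It removes a common trend, not trends that differ between waves.

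Cost: a weaker headline claim and some extra analysis for items 1 and 2, using surveys already planned. Item 3 adds one survey round, some survey burden and earlier naming of sites.

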In 2020 members of our team led a nationwide survey of NZ ED staff (n=1,372) to determine rates of burnout. In 22 EDs 711 (52%) nurses, 364 (27%) doctors, and 295 (22%) auxiliary staff were recruited. Overall rates of burnout, as determined by the Copenhagen Burnout Inventory (CBI),³ were very high with 59.5% reporting personal burnout, 54.7% reporting work-related burnout and 19.4% reporting patient-related burnout. Of the three worker cohorts, nurses reported the highest proportion of burnout with 68.8%, 63.0% and 25.8% for personal, work-related, and patient-related domains respectively. These findings are higher than rates seen in Australasian EM doctors, Danish human service sector staff and NZ senior medical officers (Table 5).

Table 5 Percentage of staff burnout in NZ ED staff compared with other cohorts

| CBI Burnout Domain | NZ ED staff 2020¹¹ n=1,372 % (mean, SD) | NZ SMOs 2020²⁹ n=2,102 | NZ SMOs 2015³⁰ n=1,487 | Australasian EM doctors 2019³¹ n=729 | Danish human service sector staff 2004³² n=1,917 |
|---------------------------|---|---|---|---|---|
| Personal | 59.5% (51.5, 17.7) | 49.3% | 50.1% | 45% | 22.2% |
| Work-related | 54.7% (49.9, 19.1) | 43.5% | 42.0% | 50% | 19.8% |
| Patient-related | 19.4% (31.0, 18.9) | 16.7% | 15.7% | 13% | 15.9% |

NZ=New Zealand; ED=Emergency Department; CBI=Copenhagen Burnout Inventory; SMOs=Senior Medical Officers; SD=Standard Deviation.

Post COVID-19 pandemic, the US Surgeon General has identified healthcare worker burnout as one of four priority areas in healthcare in USA.³³ In NZ, our new health system (Te Whatu Ora, Te Aka Whai Ora) identifies “develop an inclusive health workforce” as one of six priority actions.³⁴

Solutions

Problems with workplace wellbeing and burnout are complex, multi-factorial, with no easy solutions.²⁰ While there is a paucity of high-quality evidence involving our population (staff who work in emergency departments) an outline of salient literature and concepts related to interventions to improve wellbeing and reduce burnout in healthcare staff assists directing future research.

Emergency Department Setting

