This intervention requires significant buy-in by all parties, particularly those in leadership positions within the ED and elsewhere within HCOs. Criteria for site selection are based on our previous research. As suggested by Shah,⁹⁷ and consistent with the theory of Diffusion of Innovations,⁹⁸ those departments that self-select, have relatively stable leadership, and are in the best position to make the required changes will be selected initially. It is hoped that feasibility and success at these "innovator" and "early adopter" sites will encourage an "early majority" to participate at a later date.

Eligibility Criteria for an Emergency Department to be a Study Site

Inclusion

1. Hospitals with an ED census of >5,000 presentations per year, (n=35 potential sites).
2. A LCG able to facilitate the implementation of the intervention.
3. Agreement from ED medical and nursing directors to support the intervention within current ED projects and to attempt to implement any suggested changes.
4. Ability to provide departmental data.
5. Executive agreement, at the directorate level and hospital level.
6. Locality approval for research

Exclusion

1. Be averse to implementing the intervention
2. Inability to provide departmental data.

Eligibility Criteria for individual staff to participate in research (answer surveys)

Inclusion

1. identify as a member of the ED staff and work there regularly
 - a. at least 1 shift per fortnight, or equivalent
2. current member of ED staff

Exclusion

1. ED is not considered primary place of work, outside the home

Outcome

Primary outcome

Mean change in CBI³ (work-related burnout domain) of all ED staff (nurse, doctor, other clinical, other non-clinical) 12 months post roll-out of intervention.

Secondary outcomes

Secondary outcomes are for all ED staff and each staff subgroup (nurse, doctor, other clinical, other non-clinical)

ED Staff

- Mean change in CBI (personal and patient-related domains) at 12 months.
- Utrecht Work Engagement Scale (UWES) 9-item short form⁹⁹ at 0 and 12 months.
- Psychological empowerment in the workplace¹⁰⁰ at 0 and 12 months.
- Mean change in WHO-5 Wellbeing Index (general wellbeing)¹⁰¹ at 12 months.

Department

- Number of issues raised via QILS
 - by staff
 - by patients, whānau and carers
- Number of QILS solutions
- Departmental demographics
 - patient census,
 - triage proportions,
 - triage time compliance,
 - admission rate,
 - intensive care unit (ICU) admission rate,

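### The stated primary model uses neither the individual linkage nor work group, so if all respondents are analysed a change in who answers can be counted as an intervention effect

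*Protocol*

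**What the plan says.** The primary outcome (Outcome, Primary outcome) is "Mean change in CBI³ (work-related burnout domain) of all ED staff (nurse, doctor, other clinical, other non-clinical) 12 months post roll-out of intervention". The design is before-and-after without a control group (Study Design).

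Both surveys go out by REDCap public link and answering is voluntary. Under Recruitment, "Participation of staff will rely upon local champions".

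Under Statistical methods the outcomes, primary as well as secondary, "will be compared pre and post intervention using a general linear mixed model with site as a random factor". Work group enters the primary outcome only through additional analyses (nurse against other) that test for differential effects.

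The same section says that linking each person's two surveys is needed for a sound assessment. It gives a two-question matching key, with gender and profession as tie-breakers. The follow-up survey asks about earlier participation and allows No and Unsure, so unlinked respondents are expected. The demographic questions, including work group, are the same at both surveys. The text says the answers can be matched. It does not say whether the primary analysis uses matched pairs only or everyone who answered.

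For departmental data, Data collection lists "Routine ED data for triage compliance, did not wait rate, ED LOS, staff absence and resignations and Te Tumu Whakarae targets". The secondary outcomes add items such as vacancies. Neither list includes the number of eligible staff by work group.

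**The concern.** The model as worded compares the mean of those who answered before with the mean of those who answered after, allowing for site. That contrast equals a change in burnout only if the two sets of respondents are comparable. The protocol's own background gives reason for care: in 2020 "nurses reported the highest proportion of burnout with 68.8%, 63.0% and 25.8% for personal, work-related, and patient-related domains respectively", against 54.7% work-related burnout overall. If nurses make up a different share of respondents at 12 months, the mean moves although nobody's burnout has changed. With no comparator, that movement cannot be told apart from an effect of the package.

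The protocol already collects what would limit this, namely a linkage key and work group at both surveys. The stated model uses neither. A biased estimate and an inflated false-positive rate for the primary test are at stake.

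**Working it through.** **The plan's own figure.** Under Power, "A sample size of 900 staff participants over 8 EDs will have 90% power" for a change of 5 points, two-sided alpha 0.05. No SD is given there. With SD 19.1 from Table 5 and two separate samples, n per survey = 2 × 19.1² × (1.960 + 1.282)² / 5² ≈ 307. So 450 per survey gives 97.5% power and 900 per survey over 99.9%. The stated 90% follows only with an unstated input, such as SD 23.1 at 450 per survey. On these inputs 900 is not too few. The text does not say whether 900 means responses in total or per survey, so both 450 and 900 per survey are used below.

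**Gap between nurses and other staff** (Introduction, Background: 711 nurses of 1,372; 63.0% of nurses and 54.7% of all staff with work-related burnout).
- Nurse share: 711/1372 = 0.518.
- Other staff: (0.547 − 0.518 × 0.630) / (1 − 0.518) ≈ 0.458.
- Group means are not given, so a normal approximation is used. The normal quantiles of 0.630 and 0.458 are 0.332 and −0.106, a gap of 0.438 SD.
- 0.438 × 19.1 ≈ 8.4 points. With the smaller within-group SD instead, the gap is 8.2.

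**Effect of a shift in respondent mix.** Spurious change = shift in nurse share × gap. SE of the pre/post difference = 19.1 × √(2/n), which is 1.27 at n = 450 and 0.90 at n = 900. False-positive rate = P(|Z + bias/SE| > 1.96). The shifts are assumptions. The ranges cover a gap of 8.0 to 8.4.

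| Shift in nurse share | Spurious change | False positives, 450 per survey | False positives, 900 per survey |
|---|---|---|---|
| 10 percentage points | 0.80-0.84 | 9.6-10.1% | 14.4-15.3% |
| 20 percentage points | 1.60-1.67 | 24-26% | 43-46% |

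**Simulation check.** No intervention effect, gap 8.2, 8 sites, assumed ICC 0.01, 300 runs per scenario, a site random intercept, and 448 or 896 responses per survey.

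| Nurse share at follow-up (52% at baseline) | Stated model: mean estimate | Stated model: rejection | With nurse/other term: mean estimate | With nurse/other term: rejection |
|---|---|---|---|---|
| 42%, n = 448 | −0.84 | 9.7% | 0.00 | 6.7% |
| 42%, n = 896 | −0.73 | 14.0% | +0.08 | 6.0% |
| 32%, n = 448 | −1.62 | 26.3% | +0.03 | 3.0% |
| 32%, n = 896 | −1.67 | 44.0% | −0.07 | 6.3% |

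With 300 runs, a true 5% rate has a simulation standard error of about √(0.05 × 0.95/300) = 1.3 percentage points. The adjusted rates are therefore compatible with 5%.

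**Upper limit of the mix effect.** 5 / 8.2 = 0.61, so a 61-point shift would be needed to create 5 points. From a 52% nurse share this is out of reach: losing every nurse gives 0.52 × 8.2 ≈ 4.3.

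**Selection on burnout itself.** Suppose 20% of baseline respondents are lost and the tendency to be lost correlates 0.2 to 0.5 with the score (assumed). The mean of those who remain falls by ρ × 19.1 × φ(0.842)/0.80 = ρ × 19.1 × 0.350, or 1.3 to 3.3 points. A work-group term does not remove this part.

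**The case against.** The strongest objection is the linkage plan. In matched pairs the same people appear at both times, so work-group mix cannot drift. A reader might infer that a change in respondents necessarily enters the estimate and that nothing in the plan guards against it. The documents do not support that. The problem arises if all respondents are analysed, which the text leaves open. What stands is that the stated model has no participant term and the analysis set is not fixed. A pairs-only analysis would instead describe people who answered twice, which is narrower than all ED staff.

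A reader might also infer that drift in respondent mix would be invisible. It would not be, because work group is asked at both surveys. The planned nurse-against-other analysis would also help to reveal a mix artefact, although it leaves the primary estimate unadjusted. Only the response fraction needs a headcount.

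A third inference would be that reliance on local champions makes the sample selective. The plain-English summary speaks of surveying all ED staff and has Local Investigators leading data collection. Nothing says the link bypasses part of the staff list, so changing the distribution route would be a preference about conduct.

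Finally, covariates are often left to a statistical analysis plan, and one may exist. This carries weight, and leaving covariates unlisted would not be an error by itself. The point here is narrower: the protocol does state a model, and that model does not use the linkage the same section calls necessary.

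**Conclusion.** The concern holds in conditional form. If all respondents are analysed with the stated model, a change in who answers can be counted as an intervention effect. The size is about 0.8 points per 10-point shift in nurse share. That is roughly one-sixth of the 5 points called clinically significant, but enough to double or triple the nominal 5% error rate. A claim that the error rate simply exceeds 5% would go too far, because it does so only if the mix shifts.

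The figures rest on the 2020 survey carrying over, a normal approximation for the gap, the two surveys treated as separate samples, and assumed shifts. The protocol gives no information on the likely shift or its direction, so the bias could hide a benefit as well as mimic one.

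**What to change.** 1. In the primary model, add work group (four levels) as a fixed effect, optionally with gender and ethnicity, and a participant random intercept based on the linkage key. State that all respondents are included. The cost is model wording only, since the data are already collected.
2. Give the linked-pairs estimate as a pre-specified sensitivity analysis. This needs no new data.
3. Do not adjust for years at current ED. Everyone who stays gains a year between surveys, so it is entangled with period, and the package may itself change retention.
4. Optionally, obtain from each ED the number of eligible staff by work group when each survey opens. Report response fractions and a headcount-weighted estimate as a sensitivity analysis. The cost is a small table per ED per survey and a slightly wider interval for that estimate.
5. State as a limitation that none of this removes selection on burnout, within a work group, among people who answer only once.

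No extra participants are needed.
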